8. STUDY ASSESSMENTS AND PROCEDURES

The investigator (or an appropriate delegate at the investigator site) must obtain a signed and dated ICD before performing any study-specific procedures.

Study procedures and their timing are summarized in the SoA. Protocol waivers or exemptions are not allowed.

PFIZER CONFIDENTIAL

Immediate safety concerns should be discussed with the sponsor immediately upon occurrence or awareness to determine if the participant should continue or discontinue study intervention.

Adherence to the study design requirements, including those specified in the SoA, is essential and required for study conduct.

All screening evaluations must be completed and reviewed to confirm that potential participants meet all eligibility criteria. The investigator will maintain a screening log to record details of all participants screened and to confirm eligibility or record reasons for screening failure, as applicable.

Every effort should be made to ensure that protocol-required tests and procedures are completed as described. However, it is anticipated that from time to time there may be circumstances outside the control of the investigator that may make it unfeasible to perform the test. In these cases, the investigator must take all steps necessary to ensure the safety and well-being of the participant. When a protocol-required test cannot be performed, the investigator will document the reason for the missed test and any corrective and preventive actions that he or she has taken to ensure that required processes are adhered to as soon as possible. The study team must be informed of these incidents in a timely manner.

For samples being collected and shipped, detailed collection, processing, storage, and shipment instructions and contact information will be provided to the investigator site prior to initiation of the study.

In the case of extreme circumstances, such as natural disasters or a pandemic, visits for follow-up or procedures may need to be conducted through other means (eg, telephone, home visits).

8.1. Efficacy Assessments

8.1.1. Immunogenicity Assessments

Blood samples (Cohorts 1 and 2: approximately 5 mL per sample; Cohorts 3 and 4: approximately 10 mL per sample) will be collected from all participants prior to vaccination at Visit 1 and at Visit 2 (1 month after vaccination). These are the immunogenicity time points.

The total blood sampling volume for individual participants in this study is approximately 10 mL in children \geq 15 months to $<$ 5 years of age (Cohorts 1 and 2), and 20 mL in children and adolescents \geq 5 to $<$ 18 years of age (Cohorts 3 and 4).

Pneumococcal Responses

IgG Responses to the 20 Pneumococcal Serotypes Contained in 20vPnC

IgG antibody concentrations for serotypes present in 20vPnC (1, 3, 4, 5, 6A, 6B, 7F, 8, 9V, 10A, 11A, 12F, 14, 15B, 18C, 19A, 19F, 22F, 23F, and 33F) will be determined on all sera collected at the 2 immunogenicity time points (Visits 1 and 2). The serotype-specific IgG concentrations will be measured by Pfizer's multiplex Luminex immunoassay.

OPA Responses to the 20 Pneumococcal Serotypes Contained in 20vPnC

OPA titers for serotypes present in 20vPnC (1, 3, 4, 5, 6A, 6B, 7F, 8, 9V, 10A, 11A, 12F, 14, 15B, 18C, 19A, 19F, 22F, 23F, and 33F) will be determined in randomly selected subsets of sera for the immunogenicity time points (Visits 1 and 2). These subsets will be randomly selected, by an unblinded third party, to ensure that each subset has equal representation of both vaccine groups. Further details will be described in the clinical specimen assessment plan (CSAP). The serotype-specific OPA titers will be measured by Pfizer's OPA assay.

CCI

8.1.2. Biological Samples

Blood samples will be used only for scientific research. Each sample will be labeled with a code so that the laboratory personnel testing the samples will not know the participant's identity. Samples that remain after performing assays outlined in the protocol may be stored by Pfizer. Unless a time limitation is required by local regulations or ethical requirements, the samples will be stored for up to 15 years after the end of the study and then destroyed.

No testing of the participant's genetic material will be performed.

The participant's parent(s)/legal guardian(s) may request that the participant's samples, if still identifiable, be destroyed at any time (depending on the age of the participant and according to local requirements, participants may also request that their samples be destroyed); however, any data already collected from those samples will still be used for this research. The biological samples may be shared with other researchers as long as confidentiality is maintained and no testing of the participant's genetic material is performed.

8.2. Safety Assessments

A clinical assessment, including medical history and measurement of temperature as appropriate for the age of the child, according to routine local practice will be performed on all participants prior to vaccination to determine participant eligibility and to establish a clinical baseline. Significant medical history and significant findings from any physical examination (if performed) will be recorded as medical history in the CRF. Temperature measurement prior to vaccination will be documented and recorded in the CRF.

The participant will be observed for 30 minutes after study vaccination and any reactions during the visit will be assessed and recorded.

Prompted e-diary events, including local reactions (redness, swelling, and pain at the injection site) and systemic events (Cohort 1: fever, decreased appetite, drowsiness/increased sleep, and irritability; Cohorts 2-4: fever, fatigue, headache, muscle pain, and joint pain) that occur within 7 days following investigational product administration (Days 1 to 7, where Day 1 is the day of vaccination) are graded as described in [Section 8.2.2](#). Furthermore, AEs, SAEs, and NDCMCs will be collected as defined in [Section 10.3](#).

Planned time points for all safety assessments are provided in the SoA. Unscheduled clinical laboratory measurements may be obtained at any time during the study to assess any perceived safety concerns.

8.2.1. Participant Electronic Diary

The participant's parent(s)/legal guardian(s) will be asked to monitor and record local reactions, specific systemic events, fever, and antipyretic/pain medication taken for 7 days, each evening following the study vaccination using an e-diary (in a provisioned device or application on a personal device). This allows recording of these assessments only within a fixed time window, thus providing an accurate representation of the participant's experience. Data on local reactions, specific systemic events, fever, and use of antipyretic/pain medication reported in the e-diary will be transferred electronically to the e-diary vendor, where they will be available for review by investigators, their qualified designees, and sponsor staff at all times via an internet-based portal. At intervals agreed to by the vendor and Pfizer, these data will be transferred electronically to Pfizer for analysis and reporting.

The daily e-diary data will not be captured in the CRF. However, if a participant is withdrawn because of prompted events reported in the e-diary, the event(s) should be recorded on the AE page of the CRF, regardless of whether the investigator considers the event(s) to be clinically significant.

The investigator or designee must obtain stop dates for any local reactions or specific systemic events ongoing on the last day that the e-diary was completed. The stop dates should be entered in the CRF.

Investigators (or an appropriately qualified designee) are required to review the e-diary data online at frequent intervals (daily is optimal) to evaluate participant compliance and reported events as part of the ongoing safety review.

8.2.2. Grading Scale for Prompted Events

The grading scales used in this study to assess prompted events as described below are based on concepts outlined in the Food and Drug Administration (FDA) Center for Biologics Evaluation and Research (CBER) guidelines on toxicity grading scales for adults and adolescent volunteers enrolled in preventive vaccine clinical trials,⁷⁵ but have been adapted for applicability to healthy infants.

8.2.2.1. Local Reactions

For the first 7 days following the study vaccination (Days 1 through 7, where Day 1 is the day of vaccination), the participant's parent(s)/legal guardian(s) will be asked to assess redness, swelling, and pain at the injection site (left leg [option for Cohort 1 only] or left arm) and to record the symptoms in the e-diary in the evening. Redness and swelling will be measured and recorded in measuring device (caliper) units (range: 1 to >14; an entry in the e-diary of 15 will denote >14), and then categorized during analysis as mild, moderate, or severe based on the grading scales in [Table 1](#) below. Measuring device units can be converted to centimeters according to the following scale: 1 measuring device unit = 0.5 cm. Pain at the vaccine injection site will be assessed by the participant's parent(s)/legal guardian(s) as mild, moderate, or severe according to the grading scales in [Table 1](#) below. The participant's parent(s)/legal guardian(s) will be prompted to contact the investigator if the participant experiences a severe (Grade 3 or above) local reaction to assess the reaction and perform an unscheduled assessment or visit as appropriate.

Only an investigator is able to classify a participant's local reaction as Grade 4, after physical examination of the participant or documentation from another medically qualified source (eg, emergency room or hospital record). If a participant experiences a Grade 4 local reaction, the investigator must immediately notify the sponsor. Site staff will educate the participant's parent(s)/legal guardian(s) regarding signs and symptoms that would prompt site contact.

The procedure for notification of the sponsor is provided in the ISF or equivalent.

Table 1. Grading Scales for Local Reactions in Study Participants

Local Reaction	GRADE 1 Mild	GRADE 2 Moderate	GRADE 3 ^a Severe	GRADE 4 ^b
Redness	1 to 4 caliper units (or measuring device units) = >0 to 2.0 cm	5 to 14 caliper units (or measuring device units) = >2.0 to 7.0 cm	>14 caliper units (or measuring device units) = >7.0 cm	Necrosis or exfoliative dermatitis ^b
Swelling	1 to 4 caliper units (or measuring device units) = >0 to 2.0 cm	5 to 14 caliper units (or measuring device units) = >2.0 to 7.0 cm	>14 caliper units (or measuring device units) = >7.0 cm	Necrosis ^b
Pain at injection site (tenderness)	Cohort 1: Hurts if gently touched (eg, whimpers, winces, protests, or withdraws) Cohorts 2-4: Does not interfere with activity	Cohort 1: Hurts if gently touched with crying Cohorts 2-4: Interferes with activity	Cohort 1: Causes limitation of limb movement Cohorts 2-4: Prevents daily activity ^c	Emergency room visit or hospitalization for severe pain (tenderness) at injection site

Abbreviations: CRF = case report form; e-diary = electronic diary.

Note: If the size of the redness and/or swelling falls between 2 measuring device units, the higher measuring device unit number will be recorded in the e-diary.

- Parent(s)/legal guardian(s) of the participants experiencing local reactions >14 caliper units (>7.0 cm) are to be contacted by the study site. An unscheduled visit may be required.
- Grade 4 assessment should be made by the investigator. Grade 4 will not be collected in the e-diary but will be collected as an AE in the CRF. The severity of the local reaction should be graded using the AE grading scale in [Section 10.3.4](#).
- Prevents daily activity, eg, results in missed days of work or school or is otherwise incapacitating.

8.2.2.2. Systemic Events – Symptoms and Fever

8.2.2.2.1. Symptoms

For the first 7 days following the study vaccination (Days 1 through 7, where Day 1 is the day of vaccination), the participant's parent(s)/legal guardian(s) will be asked to assess decreased appetite, drowsiness/increased sleep, and irritability in Cohort 1, and fatigue, headache, muscle pain, and joint pain in Cohorts 2 through 4, and to record the symptoms in the e-diary (in a provisioned device or application on a personal device) in the evening. The symptoms will be assessed by the participant's parent(s)/legal guardian(s) as mild, moderate, or severe according to the grading scales in [Table 2](#) and [Table 3](#) below. The participant's parent(s)/legal guardian(s) will also be instructed to contact site staff if the participant

experiences any possible Grade 4 prompted systemic event (ie, emergency room visit or hospitalization for severe decreased appetite, severe drowsiness/increased sleep, or severe irritability) for 7 days following vaccination. Study staff may also contact the participant's parent(s)/legal guardian(s) to obtain additional information on Grade 3 events entered into the e-diary.

Only an investigator is able to classify a participant's systemic event as Grade 4, after physical examination of the participant or documentation from another medically qualified source (eg, emergency room or hospital record) or telephone contact with the participant's parent(s)/legal guardian(s). If a participant experiences a Grade 4 systemic event, the investigator must immediately notify the sponsor.

The procedure for notification of the sponsor is provided in the study reference manual (SRM) or equivalent.

Table 2. Grading Scales for Systemic Events - Participants Who Are ≥ 15 Months to <2 Years of Age (Cohort 1)

Systemic Event	GRADE 1 Mild	GRADE 2 Moderate	GRADE 3 Severe	GRADE 4 ^a
Decreased appetite (loss of appetite)	Decreased interest in eating	Decreased oral intake	Refusal to feed	Emergency room visit or hospitalization for severe decreased appetite (loss of appetite)
Drowsiness (increased sleep)	Increased or prolonged sleeping bouts	Slightly subdued interfering with daily activity	Disabling not interested in usual daily activity	Emergency room visit or hospitalization for severe drowsiness (increased sleep)
Irritability (fussiness) (synonymous with restless sleep; decreased sleep)	Easily consolable	Requiring increased attention	Inconsolable; crying cannot be comforted	Emergency room visit or hospitalization for severe irritability (fussiness)

Abbreviations: CRF = case report form; e-diary = electronic diary.

a. Grade 4 assessment should be made by the investigator. Grade 4 will not be collected in the e-diary but will be collected as an AE in the CRF. The severity of the systemic event should be graded using the AE severity grading scale provided in [Section 10.3.4](#).

Table 3. Grading Scales for Systemic Events - Participants Who Are ≥ 2 to <18 Years of Age (Cohorts 2-4)

Systemic Event	GRADE 1 Mild	GRADE 2 Moderate	GRADE 3 Severe ^a	GRADE 4 ^b
Fatigue (= tiredness in diaries)	Does not interfere with activity	Some interference with activity	Prevents daily routine activity	Emergency room visit or hospitalization for severe fatigue
Headache	Does not interfere with activity	Some interference with activity	Prevents daily routine activity	Emergency room visit or hospitalization for severe headache
Muscle pain	Does not interfere with activity	Some interference with activity	Prevents daily routine activity	Emergency room visit or hospitalization for severe muscle pain
Joint pain	Does not interfere with activity	Some interference with activity	Prevents daily routine activity	Emergency room visit or hospitalization for severe joint pain

Abbreviations: CRF = case report form; e-diary = electronic diary.

- Prevents daily routine activity, eg, results in missed days of work or school or is otherwise incapacitating; includes use of narcotics for analgesia.
- Grade 4 assessment should be made by the investigator. Grade 4 will not be collected in the e-diary but will be collected as an AE in the CRF. The severity of the systemic event should be graded using the AE severity grading scale provided in [Section 10.3.4](#).

8.2.2.2.2. Fever

In order to record information on fever, a digital thermometer will be given to the participant's parent(s)/legal guardian(s) with instructions on how to measure temperature at home. Temperature will be collected in the evening, daily, for 7 days following the study vaccination (Days 1 through 7, where Day 1 is the day of vaccination) and at any time during the 7 days that fever is suspected. Fever is defined as a temperature of $\geq 38.0^{\circ}\text{C}$ ($\geq 100.4^{\circ}\text{F}$). The highest temperature for each day will be recorded in the e-diary. In the event of a fever on Day 7, temperature will be collected daily until fever has resolved (1 day of temperature less than 38.0°C [100.4°F]) in order to collect a stop date in the CRF. A participant's parent(s)/legal guardian(s) will be prompted to contact the investigator if the participant experiences a fever $>40.0^{\circ}\text{C}$ ($>104.0^{\circ}\text{F}$) to assess the fever and perform an unscheduled assessment, as applicable (see [Section 8.10.4](#)). Study staff may also contact the participant's parent(s)/legal guardian(s) to obtain additional information if a temperature of $>38.9^{\circ}\text{C}$ ($>102.0^{\circ}\text{F}$) is entered into an e-diary. Temperature will be measured and recorded to 1 decimal place and then grouped into ranges for the analysis; see [Table 4](#) below.

Table 4. Ranges for Fever

≥38.0°C to 38.4°C
>38.4°C to 38.9°C
>38.9°C to 40.0°C
>40.0°C

Note: Fever is defined as temperature ≥38.0°C.

8.2.2.3. Use of Antipyretic/Pain Medication

The participant's parent(s)/legal guardian(s) will be asked to record the use of antipyretic/pain medication (yes/no) in the e-diary (in a provisioned device or application on a personal device) in the evening, daily, for 7 days following vaccination, where Day 1 is the day of vaccination.

8.2.3. Clinical Safety Laboratory Assessments

Clinical safety laboratory tests are not required by this protocol.

If laboratory values from non-protocol-specified laboratory assessments performed at the institution's local laboratory require a change in participant management or are considered clinically significant by the investigator (eg, SAE or AE or dose modification), then the results must be recorded in the CRF.

8.2.4. Pregnancy Testing (If Applicable)

Urine pregnancy tests will have a sensitivity of at least 25 mIU/mL. Pregnancy tests will be performed in women of childbearing potential (WOCBP) at the times listed in the SoA, immediately before the administration of the vaccine. A negative pregnancy test result will be required prior to the participant's receiving the investigational product. Pregnancy tests may also be repeated if requested by institutional review boards (IRBs)/ethics committees (ECs) or if required by local regulations. In the case of a positive confirmed pregnancy, the participant will be withdrawn from administration of investigational product and from the study.

8.3. Adverse Events and Serious Adverse Events

The definitions of an AE and an SAE can be found in [Appendix 3](#).

AEs will be reported by the participant's parent(s)/legal guardian(s).

Events that, in the clinical judgment of the investigator, are 1) consistent with normal growth and development and 2) do not differ significantly in frequency or severity from expected, are not generally to be considered adverse events. Examples may include, but are not limited to, teething, contact diaper rash, spitting up, colic, or typical fussiness/crying in infants and children.

The investigator and any qualified designees are responsible for detecting, documenting, and recording events that meet the definition of an AE or SAE and remain responsible to pursue and obtain adequate information both to determine the outcome and to assess whether it meets the criteria for classification as an SAE or caused the participant to discontinue from the study (see [Section 7](#)).

Each parent/legal guardian will be questioned about the occurrence of AEs in a nonleading manner. In addition, the investigator may be requested by Pfizer Safety to obtain specific follow-up information in an expedited fashion.

8.3.1. Time Period and Frequency for Collecting AE and SAE Information

The time period for actively eliciting and collecting AEs and SAEs (“active collection period”) for each participant begins from the time the participant’s parent(s)/legal guardian(s) provides informed consent, which is obtained before the participant’s participation in the study (ie, before undergoing any study-related procedure and/or receiving investigational product), through and including Visit 2. At Month 6 (final telephone contact), the participant’s parent(s)/legal guardian(s) will be contacted by telephone to collect information about SAEs, including hospitalizations and NDCMCs, since Visit 2.

Follow-up by the investigator continues throughout and after the active collection period and until the event or its sequelae resolve or stabilize at a level acceptable to the investigator, and Pfizer concurs with that assessment.

For participants who are screen failures, the active collection period ends when screen failure status is determined.

If the participant is withdrawn from the study and their parent(s)/legal guardian(s) also withdraws consent for the collection of future information, the active collection period ends when consent is withdrawn.

If a participant definitively discontinues or temporarily discontinues study intervention because of an AE or SAE, the AE or SAE must be recorded on the CRF and the SAE reported using the Vaccine SAE Reporting Form.

Investigators are not obligated to actively seek AEs or SAEs after conclusion of the study participation. However, if the investigator learns of any SAE, including a death, at any time after a participant has completed or withdrawn early from the study, and he/she considers the event to be reasonably related to the study intervention or study participation, the investigator must promptly notify the sponsor.

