On Day 1 of the study (Visit 1), participants will be assessed for eligibility and information will be collected including medical history and 13vPnC vaccination history (see [Section 6.5.3](#)). Blood will be collected prior to vaccination for immunogenicity assessments. Participants will receive a single dose of 20vPnC, which will be prepared and administered by a qualified site staff member or qualified designee. Permitted routine pediatric vaccines (see [Section 6.5.2](#)) may be given at the same time as study vaccination according to local or national recommendations, if not feasible to separate from the 20vPnC. Participants will be observed for 30 minutes after vaccination and any reactions occurring during that time will be recorded as AEs. The participant's parent(s)/legal guardian(s) will be provided with an e-diary (or e-diary application), thermometer, and measuring device and instructed to collect prompted local reactions (redness, swelling, and pain at the injection site) and age-applicable systemic events (fever, decreased appetite, drowsiness/increased sleep, and irritability in Cohort 1; and fever, fatigue, headache, muscle pain, and joint pain in Cohorts 2-4) for 7 days following vaccination. Use of antipyretic/pain medications will also be prompted for and collected daily in the e-diary for 7 days after vaccination. The participant's parent(s)/legal guardian(s) will be instructed to contact the study staff if the participant experiences severe redness or swelling > 14 caliper units, severe pain at the injection site, or fever $> 40.0^{\circ}\text{C}$ ($> 104.0^{\circ}\text{F}$), or has an emergency room visit or hospitalization.

Participants will return for Visit 2, approximately 1 month (28 to 42 days) after Visit 1 (study Day 29 to 43). Information will be collected from the participant's parent(s)/legal guardian(s) on AEs, including nonserious AEs, SAEs, and NDCMCs, and e-diary follow-up (as needed). Concomitant medications used to treat SAEs or NDCMCs occurring after the previous visit will be recorded. Information on vaccines given since the previous visit will also be recorded. Blood will be collected for immunogenicity assessments.

Participants will have Visit 3, approximately 6 months (168 to 196 days) after Visit 1. The sites will contact the participant's parent(s)/legal guardian(s) via telephone to inquire about SAEs and NDCMCs and concomitant medications used to treat SAEs or NDCMCs since the previous visit.

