- Record AEs, SAEs, and NDCMCs during the visit as described in [Section 8.3](#) and record concomitant medications as described in [Section 6.5.3](#).
- The investigator or an authorized designee completes the CRF and updates the investigational product accountability records.
- The investigator or appropriately qualified designee reviews the e-diary data online at frequent intervals for the 7 days following vaccination to evaluate participant compliance and as part of the ongoing safety review.

8.10.2. Visit 2 (Follow-up: 28 to 42 Days After Visit 1, ie, Study Day 29 to 43)

- Record nonstudy vaccinations administered since Visit 1, as described in [Section 6.5.3](#).
- Perform a contraception check (see [Section 10.4](#)), if applicable (Cohort 3 and Cohort 4 only).
- Ensure and document that the participant continues to be eligible for the study (see [Section 7.2](#) for participant discontinuation/withdrawal) and that the temporary delay criteria for the immunogenicity blood draw are not met.
- Review the participant's e-diary data with the participant's parent(s)/legal guardian(s); collect stop dates of any e-diary events ongoing on the last day that the e-diary was completed and record stop dates in the CRF.
- Collect the e-diary (if applicable).

PFIZER CONFIDENTIAL

- Determine whether any AEs (includes nonserious AEs, SAEs, and NDCMCs) have occurred since the previous visit and follow up on any previously reported events to determine the outcome (ie, record stop dates or confirm if they are still continuing) and record as described in [Section 10.3](#) and record concomitant medications used to treat NDCMCs and SAEs.
- Collect a blood sample of approximately 5 mL for Cohorts 1 and 2, and approximately 10 mL for Cohorts 3 and 4, for immunogenicity (a topical anesthetic is permitted).
- Remind the participant or the participant's parent(s)/legal guardian(s) to contact the investigator or investigator site staff as soon as possible if any significant illness or medical event (eg, emergency room visit or hospitalization) occurs.
- Confirm whether the parent(s)/legal guardian(s) still possesses the participation contact card.
- The investigator or an authorized designee completes the CRF and the source documents.

[figure not shown]
8.10.3. Visit 3 (6-Month Safety Collection [Telephone Contact] – 168 to 196 Days After Visit 1)

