- Contact the participant's parent(s)/legal guardian(s) by telephone approximately 6 months after the study vaccination; this contact should be attempted for all participants who have received study vaccination, unless the participant's parent(s)/legal guardian(s) has withdrawn consent.
- Determine whether any SAEs and NDCMCs have occurred since the previous visit and follow up on any previously reported events to determine the outcome (ie, record stop dates or confirm if they are still continuing) and record as described in [Section 10.3](#) and record concomitant medications used to treat NDCMCs and SAEs.
- The investigator or an authorized designee completes the CRF and the source documents.

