4. ANALYSIS SETS (POPULATIONS FOR ANALYSIS)

Analysis populations are defined for the statistical analysis of safety and immunogenicity results in the table below.

Population	Description
Enrolled	All participants who have a signed ICD.
Evaluable immunogenicity	All participants who: 1. Are eligible, 2. Receive 20vPnC, 3. Have at least 1 valid immunogenicity result from 1 month after vaccination collected within 27 to 56 days after vaccination for Cohorts 1-2 or within 27 to 49 days after vaccination for Cohorts 3-4, and 4. Have no other major protocol deviations as determined by the clinician The evaluable immunogenicity population will be used as the primary analysis population for the pneumococcal immunogenicity results.
CCI	[REDACTED]
Safety	All participants who receive 20vPnC and have safety follow-up after vaccination.

PFIZER GENERAL BUSINESS

[REDACTED]

For the evaluable immunogenicity population definition, the blood collection window has been expanded by 1 extra day before and 14 days after the protocol-specified blood collection window of 28 to 42 days, for consistency with established rules in the Prevnar 13® development program for Cohorts 1 and 2. For Cohorts 3 and 4, the window was expanded by 1 day before and 7 days after the protocol-specified blood collection window consistent with the 20vPnC adult program. A major protocol deviation is a protocol deviation that, in the opinion of the Pfizer clinician or medical monitor, would materially affect assessment of immunogenicity, eg, participant receipt of a prohibited vaccine or medication that might affect immune response or a medication error with suspected decrease in potency of the vaccine.

CC1

E-diary data will be summarized among those in the safety population who report any e-diary data.

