6.1.1.3. Adverse Events

6.1.1.3.1. Main Analysis

- Estimands: The percentages of participants reporting AEs from vaccination to 1 month after vaccination ([Section 2.1](#)).
- Analysis set: Safety population ([Section 4](#)).
- Analysis time points: Vaccination to 1 month after vaccination.
- Analysis methodology: Descriptive statistics.
- Intercurrent events and missing data: No missing values will be imputed except for partial AE start dates ([Section 5.3](#)).
- Reporting results: The numerator (n) and the denominator (N) used in the percentage calculation, the percentage (%), and the corresponding 2-sided 95% CI for participants reporting any AE, by each system organ class and each preferred term within system organ class, will be presented by cohort.

CCI

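### If Visit 2 is missed and not recovered, no scheduled contact asks about first-month nonserious AEs, yet the child can stay in the AE denominator; the 6-month look-back is also worded inconsistently

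*Protocol*

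**What the plan says.** **Collection of AEs.** Protocol 8.3.1 runs active collection from consent "through and including Visit 2". The Visit 2 procedures in 8.10.2 tell the site: "Determine whether any AEs (includes nonserious AEs, SAEs, and NDCMCs) have occurred since the previous visit". No later scheduled contact asks about nonserious AEs.

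**The 6-month call.** It is meant to reach nearly everyone: under 8.10.3, "this contact should be attempted for all participants who have received study vaccination", unless consent has been withdrawn. Its content is limited to SAEs, NDCMCs and the medication used to treat them. The look-back is stated in two ways:
- 8.3.1: "to collect information about SAEs, including hospitalizations and NDCMCs, since Visit 2".
- 8.10.3: "Determine whether any SAEs and NDCMCs have occurred since the previous visit". Section 4.1 agrees ("to inquire about SAEs and NDCMCs and concomitant medications used to treat SAEs or NDCMCs since the previous visit"), as does the synopsis.

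**Recovery of a missed visit.** Section 7.3 requires the site to try to contact the family and rebook. Section 7.2 asks that a withdrawing child return for a final visit with the next visit's procedures, but adds that leaving withdrawal procedures undone is not a deviation.

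**Analysis.** SAP 4 defines the safety population as "All participants who receive 20vPnC and have safety follow-up after vaccination". Protocol 9.3 asks for some safety data after vaccination. SAP 6.1.1.3.1 analyses AEs in that population and states "No missing values will be imputed except for partial AE start dates". It does not define N further. E-diary summaries, by contrast, are restricted in SAP 4 to children with some e-diary data.

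**The concern.** The percentage of participants with AEs up to 1 month is a primary safety estimand. In a single-arm study that absolute percentage is itself the result; there is no control group in which the same under-collection would cancel.

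For nonserious AEs the plan relies on one visit, and that visit includes a second blood draw. A family may decline it and still answer the telephone at 6 months. Such a child has safety information and belongs to the safety population, but was not asked about ordinary illness in the first month. With no imputation and no rule on N, a child without an AE record would naturally be tabulated as a child without an AE. Any resulting error is downward.

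The same child is the one for whom the two look-backs differ. Counting from Visit 2 gives no defined start when Visit 2 did not happen. Counting from the previous visit goes back to vaccination.

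**Working it through.** **1. The plan's own figure.** Protocol Table 5 gives the chance of seeing at least one AE among 200 children, 1 − (1 − p)^200.
- p = 0.1%, 0.5%, 1%, 2% gives 18.1%, 63.3%, 86.6%, 98.2%.
- Table 5 states 18, 63, 87 and 98, so it reproduces.
- It takes all 200 as observed for AEs. With 180 asked, the values are 16.5%, 59.4%, 83.6% and 97.4%. The statement of more than 90% at a true rate of 2% still holds.

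**2. Following one child through the text.** The child is vaccinated, the e-diary is kept, Visit 2 is missed, rebooking fails, and the family is reached at 6 months.
- Nonserious AEs: the 30-minute observation is recorded, and the e-diary covers the prompted reactions for 7 days. The Visit 2 question is not asked, and the 6-month call does not contain it.
- SAEs and NDCMCs: under 8.10.3, 4.1 and the synopsis they are asked about back to Visit 1. Under 8.3.1 the start point is a visit that did not occur.
- Analysis set: e-diary data or the 6-month call satisfies both definitions of the safety population. The point does not depend on whether the 30-minute observation alone would count.

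**3. Size.** Let m be the share of the safety population not asked, and p the true AE percentage, taken to be the same in children asked and not asked. If none of the AEs in the unasked children is captured and they are counted as event-free:

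reported percentage = p × (1 − m)

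The documents give no value for m or p. Assuming p = 20%:
- m = 2%: 20 × 0.98 = 19.6%
- m = 5%: 20 × 0.95 = 19.0%
- m = 10%: 20 × 0.90 = 18.0%

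At m = 10% in a cohort of 200, 36/200 = 18.0% (95% Clopper-Pearson interval 12.9 to 24.0), against 36/180 = 20.0% (14.4 to 26.6) among those asked. With no events seen, the upper 95% limit is 1.83% on 200 and 2.03% on 180.

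The relative understatement is m when nothing is captured, and less when spontaneous reports are recorded. If children who miss Visit 2 have a higher AE risk than the rest, it could exceed m; the documents give no information on this.

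**The case against.** The case on the other side is substantial.

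- **Recovery is required.** Section 7.3 obliges the site to pursue a missed visit, and 7.2 asks for a final visit. Section 8.3 says that every parent will be questioned about AEs. It is arguable that active collection stays open until Visit 2 takes place, so an AE mentioned during a rebooking call would be recorded. Spontaneous reports are recorded under 8.3.1.2, and parents are told to call about significant illness. This stands, and it limits the gap to children whose visit is not recovered and whose AE nobody volunteers. It does not close the gap: no text tells the site to ask about AEs by telephone when the family does not come, and visits by other means are foreseen only in extreme circumstances.
- **First-month SAEs.** A reader might infer from 8.3.1 that they are lost. The documents do not support that. The synopsis, 4.1 and 8.10.3 reach back to the previous visit, and SAP 3.1.1.5 has SAEs and NDCMCs collected from consent to the end of the study.
- **Counted as event-free.** A reader might take this as written. It is an inference from the analysis set and the no-imputation rule. Redacted blocks follow the main AE analysis, so a further rule or supplementary analysis cannot be excluded.
- **The 10% allowance.** A reader might treat the step from 200 enrolled to 180 evaluable as the rate of missed Visit 2s. It covers every reason for not being evaluable, including ineligibility, invalid or out-of-window samples and major deviations.
- **Disposition.** SAP 6.5.2.1 already reports Visit 2 completion by cohort. That lets a reader approximate the number not asked, but leaves the AE percentage as it is.

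**Conclusion.** The point holds in a limited form, and it is minor. For a reachable child whose Visit 2 is missed and not recovered, no scheduled contact asks about nonserious AEs in the first month, and the visible text does not keep that child out of the AE denominator. Separately, 8.3.1 disagrees with the synopsis, 4.1 and 8.10.3 on the 6-month look-back, and these passages must be reconciled.

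On the assumed range of 2% to 10% not asked, a true 20% would be reported 0.4 to 2.0 percentage points too low. Even the larger shift lies well inside the confidence interval for one cohort. This rests on equal AE risk in asked and unasked children, on no spontaneous capture, and on unasked children being tabulated as having no event. Safety is descriptive here, so no hypothesis test is affected.

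**What to change.** 1. **Protocol 8.3.1 and 8.10.3:** use one look-back for the 6-month call, for example *since the last completed contact at which AEs were elicited*, and bring 4.1 and the synopsis into line.
2. **Protocol 8.10.3, with a cross-reference in 7.3:** for vaccinated participants who did not complete Visit 2, and whose family has not withdrawn consent for contact, ask by telephone, no later than the 6-month call, about all AEs in the first month and all SAEs and NDCMCs since vaccination.
3. **SAP 6.1.1.3:** report, by cohort, how many in the safety population had no 1-month AE inquiry, and add a supportive AE percentage with only those asked in N. State that this line assumes similar AE risk in those not asked.

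The cost is some script wording, a few calls and one extra table line. The drawback is that AEs elicited at 6 months will be recalled late and less completely, so the contact is better made as soon as the visit is known to be missed.
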